C8.o. Analysis plan for the crossover trial. Demographics and clinical data will be provided, stratified by sex as well as PAH subtype. This data will also be tracked for screen failures and drop-outs. Continuous data will be expressed as medians and ranges and categorical data will be expressed as frequency and percentages. Analyses will follow the intention-to-treat paradigm. All end points will be modeled using generalized estimating equations (GEEs), nesting repeated measures within patient and including terms for sex, age, race/ethnicity, PAH-subtype, randomization, and time point, along with all 2-way and 3-way interactions in which carry-over or period effects will be considered. Distribution will be chosen based on inspection of model residuals. Classical sandwich estimation will be used to adjust for model misspecification after maximizing the appropriateness of distribution selected. Orthogonal linear estimates will be constructed within GEEs to test each hypothesis (see Aims) and presented both as the percentage change and absolute change in RV measures (**Aim 1**), changes in NO products and ET-1 (**Aim 2**), and secondary end points. No adjustment for multiple comparisons will be made given the pilot nature of the study. The main effect of DHEA and interactions of DHEA with sex (as well as age, race/ethnicity, PAH-subtype) will be tested within models, with use of visualizations including individual scores for exploratory analysis. Hypotheses will be two-tailed.

C8.p. Sample size and power for the crossover trial. We anticipate a 10% drop-out rate and calculated power based on an anticipated sample size of 24 subjects (12 men, 12 women). As this is a pilot study, detection of a signal (even if not statistically significant) and “proof of concept” that DHEA treatment may improve RV phenotype and alter major PAH regulators would encourage the pursuit of a

larger Phase II parallel arm trial. Time by treatment and PAH subtype by treatment interactions will also be considered as part of 3-way interactions terms in GEE.

C8.p1. Aim 1: Power to detect differences in RV longitudinal strain.

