We will have excellent power to detect clinically relevant changes in RV strain ($\alpha = 0.05$) (Table 7). A $\geq 5\%$ improvement in RV strain (measured by echocardiography; less precise than MRI) occurs with approved PAH therapies and predicts clinical stabilization and survival in PAH.⁵⁶ We have more than enough power to detect this estimate, and effects even as small as 3%. We need this number of patients in order to perform sex-specific analyses (and test for treatment x sex interaction), where we will have 80% power to detect a 4% difference in sex-specific analyses with the presence of an interaction. Power for treatment x PAH subtype interactions will mirror these estimates. We will also have sufficient power to detect changes which approach clinical relevance in RVEF^{61, 139} and NT-proBNP¹⁴⁰ ($\alpha = 0.05$) (Table 8).

C8.p2. Aim 2: Power to detect differences in nitrate and ET-1 levels.

We will have excellent power to detect small ($0.05 \mu\text{M}$) differences in nitrite levels with DHEA treatment based on conservative previously observed estimates ($\alpha = 0.05$).^{25, 141} We will have excellent power to detect small (well-less than 2 pg/mL) differences in ET-1 levels with DHEA treatment ($\alpha = 0.05$). Changes of this magnitude would be consistent with clinically relevant changes in ET-1 with ERAs.¹⁴²

C9. Aim 3: PAEC response to DHEA. In order to minimize burden of the trial participants (and to guarantee more catheter tips), PAECs from men and women undergoing right heart catheterization at the RIHPHC as part of PAH diagnosis or treatment and meeting the same inclusion/exclusion criteria for the cross over trial will be included. As with our preliminary data, these experiments will be performed in our Centers of Biomedical Research Excellence in Stem Cell Biology (PI: [name], P20 GM103468) and Cardiopulmonary Vascular Biology (PI: [name]; Laboratory Core PI: [name], P20 GM103652). We will also examine the effect of DHEA on PAECs obtained from two additional sources: 1) commercially available human PAECs, 2) those obtained from the distal pulmonary circulation of PAH lung explants available through the Pulmonary Hypertension Breakthrough Initiative (PHBI) (PI [name], R24 HL123767; see letter of support).

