We will isolate PAECs and assess NO and ET-1 production at baseline and following exposure to DHEA (Figure 12). Following catheterization, the PAC tip will be placed into 1 well of a 24 well plate, with Attachment Factor Solution (Cell Applications, Inc, San Diego, CA) and media (EndoGRO, Millipore Sigma, Billerica, MA). The PAC tip will be washed with fresh media every 2 days and previous media from the tip well will be moved into a new well in the 24 well plate. Cells will be grown in primary culture to confluence (~150K-200K cells) over 2-3 weeks. Cells will then be treated with Triple Express (ThermoFisher Scientific, Waltham, MA) and transferred to T-25 and then T-75 flasks over 4-5 days; we anticipate ~5 million cells in 3-4 passages. In the event that we are unable to culture a robust number of PAECs using the above protocol, conditioned media charcoal-stripped¹⁴³ of all steroid hormones will be used.

1) NO and ET-1 synthesis. Cell lysate and culture media from cultured PAECs passage 3-5 will be snap frozen in liquid nitrogen and stored at -80°C . ET-1 and cGMP will be measured by ELISA and nitrite and nitrate levels will be quantified using tri-iodide-based reductive chemiluminescence (See Section C8.m7). Expression of eNOS, soluble guanylyl cyclase (sGC) α and β , IL-6, STAT3, and MAPK will be measured with standard RT-PCR and Western blot methods using commercial nucleic acid probes and antibodies.¹⁴⁴

2) Cell treatment. Cells will be incubated at 37°C in media in the presence or absence (controls cells) of DHEA at final concentrations of 1, 10, and $100 \mu\text{M}$ (Sigma-Aldrich, St. Louis, MO). Initial experiments will be conducted using commercially available PAECs to determine optimum cell concentration and exposure times that will provide consistent assessment of NO and ET-1 synthesis. Cell proliferation, migration, adhesion, and tube formation will be characterized before and after exposure to DHEA using standardized protocols

[figure not shown]
Table 7. Power calculations for RV strain (N = 24)

	RV strain difference, %	Power
No interaction	3.0	89%
	5.0	99%
	7.0	100%
Interaction	4.0	80%
	5.0	94%
	7.0	100%

Table 8. Power calculations for RVEF and NT-proBNP (N = 24)

	RVEF, %	Power	NT-proBNP, mg/L	Power
No interaction	5.0	80%	200	98%
Interaction	8.0	80%	200	80%

Figure 12. Schematic for Aim 3

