performed in our laboratory¹⁴⁵ with concurrent confirmation of PAEC phenotype. We will also determine the effect of DHEA in commercially available disease free PAECs. These conditions will then be used in experiments to assess DHEA's effects on NO and ET-1 synthesis in PAECs from both sexes with PAH. All experiments will be repeated with 1) exposure to E2 for comparison and 2) in PAECs from lung explants to determine if distal and proximal PAECs respond in a similar way to DHEA.

C9.a. Analysis Plan Aim 3: PAEC response to DHEA. Wilcoxon signed-rank tests and analysis of variance will be used to compare ET-1 and eNOS expression and nitrite and nitrate levels before and after DHEA treatment and across cells from men and women.

C10. Study timeline. Based on prior recruitment rates and fractions, we will be able to enroll 4-7 subjects per year as outlined in the study timeline. A five year mechanism is proposed and is needed in order to ensure adequate inclusion of men and completion of the protocol for subjects recruited later in the study period to allow adequate time for follow-up, biomarker and data analysis (which cannot be completed until all subjects enrolled later in the study complete the 42 week crossover trial protocol).

Table 9. Study timeline

	Yr 1	Yr 2	Yr 3	Yr 4	Yr 5
Start-up: Drug purity testing	Mos 1-6				
Relational trial database buildout	Mos 1-6				
Policies and Procedures, IRB approval	Mos 1-6				
Aim 1,2: Cross-over enrollment	n = 4	n = 7	n = 7	n = 6	n = 2
Aim 3: Commercial cells, PHBI	X	X	X	X	
Aim 3: PAECs, patient catheterizations	n = 15	n = 15	n = 15	n = 15	n = 15
Lab/results analysis				X	X
Manuscript/grant preparation				X	X

C11. Expected results

C11.a. Aims 1 and 2. Active treatment with DHEA will be associated with an improvement in RV strain pattern, lower ET-1 levels and higher nitrite and nitrate levels. Markers of maladaptive RV hypertrophy including oxidative stress will also be reduced. Sex

will modify these relationships, with women demonstrating a more robust response to DHEA.

C11.b. Aim 3. NO and cGMP synthesis will be higher and ET-1 secretion will be lower in PAECs from women with PAH than PAECs from men, respectively. Treatment with DHEA will increase eNOS expression and nitrite/nitrate levels and decrease ET-1 secretion. Female cells will demonstrate a more robust and distinct response to DHEA than male cells and E2 exposure respectively.

C12. Potential problems and alternative approaches

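### The Interaction rows of Tables 7 and 8 do not show treatment x sex interaction power: the tables' own figures imply about 52–61% where 80% is printed

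*Combined protocol and SAP*

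**What the plan says.** Section C8.p says the authors "calculated power based on an anticipated sample size of 24 subjects (12 men, 12 women"). Section C8.p1 then gives the reason for that number: to "perform sex-specific analyses (and test for treatment x sex interaction), where we will have 80% power to detect a 4% difference". The sentence ends by placing this difference in sex-specific analyses when an interaction is present. The next sentence adds: "Power for treatment x PAH subtype interactions will mirror these estimates".

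Tables 7 and 8, both for N = 24, print:

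| Endpoint | No interaction rows | Interaction rows |
|---|---|---|
| RV strain | 3.0: 89%; 5.0: 99%; 7.0: 100% | 4.0: 80%; 5.0: 94%; 7.0: 100% |
| RVEF | 5.0: 80% | 8.0: 80% |
| NT-proBNP | 200: 98% | 200: 80% |

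No SD, within-patient correlation or power formula accompanies them. Section C8.o plans that "interactions of DHEA with sex (as well as age, race/ethnicity, PAH-subtype) will be tested within models", with two-tailed hypotheses. Section C11.a lists effect modification by sex among the expected results: sex "will modify these relationships, with women demonstrating a more robust response to DHEA".

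**The concern.** Two different tests could stand behind a row labelled Interaction. One is the treatment effect within a single sex, a paired comparison in 12 patients. The other is the treatment x sex interaction, which compares the treatment effect in 12 men with that in 12 women. The second has a standard error √2 times that of the first and twice that of the overall effect in 24 patients, so the two cannot share power figures at the same difference.

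The row label, and the sentence carrying the figures over to subtype interactions, both point to the interaction test. The printed powers look too high for it. If so, a reader would credit the sex interaction test with at least 80% power when it has much less, and would give a null result more weight than it can bear. Effect modification by sex is a central hypothesis of the study, and Section A8 expects sex-based differences in response to inform the design of future trials.

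**Working it through.** **Inputs from the plan.** Two-sided alpha 0.05 (C8.o, C8.p1); 24 patients, 12 per sex (C8.p); the table rows above. **Assumed.** One within-patient DHEA-minus-placebo difference per patient, with the same SD in both sexes. Powers use the non-central t distribution. The planned model is a covariate-adjusted GEE, so these are approximations.

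**Step 1. SD implied by the No interaction rows.** Paired test, n = 24, SE = SD/√24, df 23, solved for the printed power:

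- Strain 3.0 at 89%: SD = 4.42
- RVEF 5.0 at 80%: SD = 8.37
- NT-proBNP 200 at 98%: SD = 233.6

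**Step 2. Try to reproduce the Interaction rows under each reading.** Within one sex, SE = SD/√12, df 11. Interaction, SE = SD × √(1/12 + 1/12), df 22. For strain, these SEs are 4.416/√12 = 1.275 and 4.416 × √(1/6) = 1.803.

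| Row | Printed | Within one sex (n = 12) | Treatment x sex (12 v 12) |
|---|---|---|---|
| Strain 4.0 | 80% | 81% | 56% |
| Strain 5.0 | 94% | 95% | 76% |
| Strain 7.0 | 100% | 99.9% | 96% |
| RVEF 8.0 | 80% | 85% | 61% |
| NT-proBNP 200 | 80% | 77% (81% by normal approximation) | 52% |

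The strain rows are reproduced, within 2 points, as a within-sex test. NT-proBNP is reproduced that way only approximately. RVEF 8.0 at 80% is reproduced by neither test; within one sex, 80% is reached at 7.44.

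**Step 3. A check that needs no SD.** Both NT-proBNP rows use a difference of 200. The main-effect power of 98% corresponds to a noncentrality of 4.19. The interaction SE is exactly double, so its noncentrality is 4.19/2 = 2.10, which gives 52%. Dividing by √2 instead, as for one sex, gives 2.97 and 77%.

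**Step 4. Reverse check.** If the Interaction rows were interaction power, they would imply SDs of 3.34 (strain), 6.68 (RVEF) and 167 (NT-proBNP). The No interaction rows would then have to read 98.8% at strain 3.0 (printed 89%), 93.9% at RVEF 5.0 (printed 80%) and more than 99.9% at NT-proBNP 200 (printed 98%).

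**Step 5. Sensitivity.**

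- Rounding of the printed No interaction powers by ±0.5 point moves interaction power only to 55.7–57.1% (strain 4.0), 60.4–61.5% (RVEF 8.0) and 49.9–54.1% (NT-proBNP 200).
- If strain 5.0 at 99% is read literally rather than as above 99%, the SD is 5.47 and interaction power at 4/5/7 falls to 40/57/85%. This SD fits the other rows worse: main-effect power at 3.0 would be 73%, not 89%.
- One-sided alpha, 13 per sex, an unpaired layout and the normal approximation were also tried. None brings the interaction test to 80% at strain 4.0, RVEF 8.0 or NT-proBNP 200.
- PAH subtype at strain 4.0 with SD 4.42: 52% for an 8:16 split and 45% for 6:18. Both splits are assumptions, because the plan gives none.

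**The case against.** The strongest reply is that Section C8.p1, read to the end of the sentence, attaches the 80% to sex-specific analyses and mentions the interaction test only in parentheses. On that reading the strain rows are right, the sample size is supported for within-sex effects, and the fault is a loose row label. A 4-point effect within one sex is also a different quantity from a 4-point difference between the sexes. RVEF 8.0 may simply be 7.44 rounded up. The SDs are back-solved rather than stated. This is also a pilot, for which Section C8.p accepts a signal that is not statistically significant, and Section C8.o makes no multiplicity adjustment.

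Much of this stands. The strain rows contain no arithmetic error if they are within-sex power, and the main-effect power is untouched. The rounding explanation for RVEF is possible, but the documents do not confirm it.

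It does not rescue the tables as written. The rows are labelled Interaction, and the following sentence explicitly presents the figures as a guide to interaction power for subtype. The interaction test is planned and no other power is given for it. The NT-proBNP rows exclude an equal-variance interaction reading without any SD. Pilot status lowers the stakes, but it does not make a stated power figure correct.

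**Conclusion.** The concern holds. The Interaction rows are not power for the treatment x sex test. That test has about 56% power at strain 4.0, 61% at RVEF 8.0 and 52% at NT-proBNP 200, where each row prints 80%. With 12 per sex, 80% power needs a difference between the sexes of about 5.3 strain points, 10 RVEF points or 280 NT-proBNP units. The expected 95% CI half-width for the sex difference in strain effect is 2.07 × 1.803 = 3.7 points, or 4.6 with SD 5.47.

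These sizes rest on the back-solved SDs, equal variance in the two sexes, and a simple paired analysis in place of the GEE, so confidence in the exact figures is moderate. The mismatch itself is firmer, because neither rounding nor the alternative strain SD brings the interaction test up to the printed values. The point should be fixed, but it does not threaten the primary analysis.

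**What to change.** 1. State, for every row of Tables 7 and 8, the SD of the within-patient difference and the test used, and say whether the strain difference is absolute or relative.
2. If the sponsor's calculations confirm it, relabel the strain and NT-proBNP Interaction rows as the effect within one sex (n = 12). Recheck RVEF 8.0 at 80%.
3. Add the interaction power separately. Unless the true SD is supplied, a conditional statement would serve: *Assuming an SD of 4.4, equal in both sexes, the treatment x sex contrast (12 v 12) has about 56%, 76% and 96% power for sex differences of 4, 5 and 7 strain points; 80% power needs about 5.3.* Show 40%, 57% and 85% under SD 5.5 as sensitivity.
4. Delete the sentence equating subtype interaction power with these estimates, or give subtype power at the expected split.
5. In Section C8.o, describe the interaction tests as exploratory and report them as estimates with 95% CIs.

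The cost is wording only, with no extra patients and no change to the primary analysis. The sponsor has to retrieve the SDs it used and accept less favourable stated power for the sex and subtype comparisons.

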Study end points are subject to measurement error and missingness. Measurement error will be minimized by using validated methods with demonstrated precision in experienced laboratory and imaging cores with QC in place. Every effort will be made to minimize missing data via study procedures, close follow-up, and subject retention efforts. Bias will be minimized by masking patients, investigators, and personal and randomizing the treatment periods. While the proposed sample size is small, the cross-over design by definition optimizes statistical efficiency and minimizes confounding given each participant is their own control and treatment order is randomized. Multiple comparisons could result in Type I error, but our power calculations are based on distinct hypotheses about RV phenotype. Because of the cross-over design, small differences are likely to be detected making Type II error unlikely.

Figure 9. Study protocol

C8.c. Subjects. We will randomize 26 subjects stratified by sex (13 women, 13 men) and PAH type (idiopathic PAH vs. other) from the Rhode Island Hospital Pulmonary Hypertension Center (RIHPHC) to active treatment (Period 1), placebo (Period 2) or to placebo (Period 1), active treatment (Period 2) (**Aims 1, 2**). PAH patients meeting the same inclusion criteria (Table 5) undergoing hemodynamics will be eligible for PAEC collection (**Aim 3**).

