C8.e. Subject recruitment and retention. The RIHPHC services a catchment area of all of Southern New England and is the only center accredited by the Pulmonary Hypertension Association as a Comprehensive Care Center in the region. The RIHPHC cares for >400 patients and offers comprehensive patient care services including diagnostic imaging, hemodynamic evaluation, a dedicated PH step-down unit, an interdisciplinary care team, and four full-time providers. The PI and staff of RIHPHC meet weekly to screen patients for enrollment in active research protocols. Eligible patients will be approached by their PAH clinician and then by the PI or research staff. Following screening and informed consent, a maximum of four weeks may lapse before randomization (baseline visit) and eligibility in order to confirm clinical stability. New or recent changes to PAH meds will be reassessed at the baseline visit. Serum pregnancy tests will be obtained at

baseline and at week 24 (after crossover) in premenopausal subjects. Retention and complete follow-up will be assured with frequent call reminders 3-5 days prior to study visits, 24/7 accessibility of research support staff, study drug adherence logs and pill counts, and monetary compensation and parking passes for study visits.

PAH in men is rare, however based on our trial enrollment over the past three years (n = 52, 25% men) and our recent study of men¹⁰¹ we anticipate recruiting 13 (50%) men during the study. Patient-level variation in end points as well as interactions by age, sex, race/ethnicity, and PAH sub-type will be assessed. We have met all of our enrollment targets for active studies, and consider this proposal a top priority for our center.

C8.f. Investigational therapy. We have already received an Investigational New Drug exemption (IND#129285) from the FDA for this study (see attached letter). We will purchase DHEA 50 mg daily tablets in a single batch from Green Mountain Pharmaceuticals (Lakewood, CO). Green Mountain is an Active Pharmaceutical Ingredient registered manufacturer with the FDA and has produced DHEA for ongoing trials at major centers including our institution (NCT01343771). Lots previously purchased

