from this manufacturer yielded >100% DHEA from an independent laboratory (FrontRangeLabs, Loveland, CO) (included with IND letter). We will also analyze and document purity in the batch purchased for this study. Study drug and placebo will be over-encapsulated by the Investigational Services Pharmacy (see letter of support). Dose, 18 week exposure and four week washout periods were chosen based on pharmacokinetics of DHEA, treatment duration required for RV changes, and early phase trial standards in endocrine and PAH.^{36, 110-113} Changes in RV function occur after just 12 weeks of PAH therapy, justifying the planned exposure period.³⁶

C8.g. Study protocol and burden. An 18 week supply of study drug will be dispensed following randomization at the baseline visit. Cardiac MRI for RV measures (Aim 1) will be assessed at baseline, week 18 and week 40, at the end of each period receiving active treatment or placebo. Laboratory (Aim1: NT-proBNP, galectin-3, RAGE, oxidative stress markers and those for safety; Aim 2: plasma NO-related markers and serum ET-1) and secondary end points will be assessed at baseline and all four study visits (Table 6). Data collection for history and physical exam, adherence, and adverse events will occur in the RIHPHC research room, followed by 6MWD in the RIHPHC hallway. Phlebotomy for study labs will be performed by trained personnel and cardiac MRI will be performed at the end of the visit in the MRI suite; labs and imaging will occur on the first floor of the same building where the RIHPHC is located. Subjects will complete the HRQOL measures on a tablet during downtime to reduce total visit time. We will offer a small meal after phlebotomy. Based on current protocols including similar tests we anticipate the total time for a study visit will be 90–120 min (visit #1, #3) and 210–240 min for visits with MRI (baseline, visit #2, #4).

C8.h. Drug and protocol adherence. Pill counts will be tracked at each visit. A phone call after visit #2 at week 18 will confirm plan for the washout period. A second call in the washout period prior to visit #3 will ensure start date for second course of study drug.

C8.i. Randomization and blinding. Randomization of drug sequence stratified by sex and PAH subtype (Period 1–Period 2; Period 2–Period 1) will be automated by a web-based program. Study personnel and

Table 6. Study protocol and end points

Timeline, week		2	18	19-22	24	40	42	Unscheduled
Study visit	Baseline	#1	#2	Washout	#3	#4		US

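### C8.p1 says subtype power will match the sex figures, but no subtype split is fixed: the 80% needs about 12 completers in a subtype, and as interaction power it fails at any split

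*Combined protocol and SAP*

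**What the plan says.** - **Group sizes by sex.** Section C8.c: "We will randomize 26 subjects stratified by sex (13 women, 13 men) and PAH type (idiopathic PAH vs. other"). Section C8.e gives the target for men: "we anticipate recruiting 13 (50%) men during the study". Section C8.p then states that the authors "calculated power based on an anticipated sample size of 24 subjects (12 men, 12 women").
- **Subtype.** C8.c names two categories, idiopathic and other, without counts. C8.i says what is stratified: "Randomization of drug sequence stratified by sex and PAH subtype". The documents give no quota, cap or expected number for either subtype.
- **Power.** Table 7 has three rows without interaction (3.0, 5.0 and 7.0 at 89%, 99% and 100%) and three labelled as interaction (4.0, 5.0 and 7.0 at 80%, 94% and 100%). The text of C8.p1 describes the 4.0 row as power in sex-specific analyses when an interaction is present, and continues: "Power for treatment x PAH subtype interactions will mirror these estimates".
- **Analysis.** C8.o tests DHEA by subtype within a GEE model, and "Hypotheses will be two-tailed". Neither an SD nor the test behind Table 7 is stated.

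**The concern.** The sentence carries figures from a factor with fixed group sizes over to one whose group sizes are open. Stratifying sequence by subtype balances the DHEA-first and placebo-first orders within each subtype. It does not determine how many patients each subtype contains.

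The sentence also speaks of interaction power, while the figures it points to appear to be power within one group of 12. Those are different quantities, and the interaction is the harder one to detect.

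C8.b and C8.o present subtype response as something the design can assess. A non-significant result in a small subtype, or a non-significant interaction, could then be read against a stated 80% that the design does not provide.

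**Working it through.** **Inputs**
- Two-sided alpha 0.05 (C8.p1, C8.o); 24 completers, 12 per sex (C8.p).
- Stated power from Table 7.
- SD of the within-patient DHEA–placebo difference: not in the documents, so solved from Table 7 (an inference).

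**Formulas**
- Within a group of n: paired t test, noncentrality λ = δ / (SD/√n), n − 1 degrees of freedom.
- Interaction between groups n₁ and n₂: two-sample t test on the within-patient differences, λ = δ / (SD·√(1/n₁ + 1/n₂)), 22 degrees of freedom when n₁ + n₂ = 24.

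**Step 1: reproduce Table 7.** With SD 4.45:

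| n | Difference | λ | Computed | Stated |
|---|---|---|---|---|
| 24 | 3.0 | 3.30 | 88.5% | 89% |
| 24 | 5.0 | 5.50 | 99.9% | 99% |
| 24 | 7.0 | 7.71 | 100% | 100% |
| 12 | 4.0 | 3.11 | 80.9% | 80% |
| 12 | 5.0 | 3.89 | 94.2% | 94% |
| 12 | 7.0 | 5.45 | 99.9% | 100% |

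All six rows agree within 1 percentage point. Any SD from 4.385 to 4.555 keeps them within 2. A 12-against-12 interaction test at SD 4.45 gives 55.8% at 4.0, and no SD fits both the 89% row at 24 patients and the 80% row read as an interaction. The rows labelled as interaction therefore behave like power within one sex.

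**Step 2: within-subtype power at 4.0 points, SD 4.45**

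| Smaller group | λ | Own variance (n − 1 df) | Pooled variance (22 df) |
|---|---|---|---|
| 12 | 3.11 | 80.9% | 84.5% |
| 11 | 2.98 | 76.6% | 81.3% |
| 10 | 2.84 | 71.6% | 77.5% |
| 8 | 2.54 | 59.0% | 68.1% |
| 6 | 2.20 | 43.0% | 55.8% |

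Over SD 4.385 to 4.555, the own-variance figures run 72.9–69.6% at 10, 60.3–57.1% at 8 and 44.0–41.4% at 6. The larger group gains: 87.4% at 14 and 91.9% at 16 with its own variance. The difference detectable with 80% power in the smaller group rises from 4.0 points at 12 to 4.4 at 10, 5.1 at 8 and 6.4 at 6 (own variance).

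**Step 3: treatment × subtype interaction power for a 4.0-point difference between subtypes, SD 4.45**

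| Split | λ | Power |
|---|---|---|
| 12/12 | 2.20 | 55.8% |
| 10/14 | 2.17 | 54.6% |
| 8/16 | 2.08 | 51.0% |
| 6/18 | 1.91 | 44.6% |

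**Step 4: how likely is 12/12?** The documents do not give the mix. Purely as an illustration, if half of eligible patients were idiopathic and 24 completed, the chance of exactly 12/12 is C(24,12)/2²⁴ = 2,704,156/16,777,216 = 16%, and the smaller group would have 10 or fewer with probability 54%.

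**The case against.** **The test and SD are inferred.** This stands. A reader might take it as established that Table 7 is a paired t test in exactly 12 patients. The documents do not say so, and 11 per group also fits the strain rows within 2 percentage points (SD 4.265 to 4.375). Twelve is used because it is the group size the plan states.

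**The plan fits one GEE model, not a t test per subtype.** If residual variance is pooled, the loss is milder, as the last column of Step 2 shows, and 11 completers would still give about 81%. Pooling softens the shortfall at 10 or fewer but does not remove it.

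**The sentence is about interactions, for which the split matters little.** Correct: going from 12/12 to 8/16 costs about 5 percentage points of interaction power. But on that reading the starting value is about 56%, so the sentence fares worse.

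**The shortfall might seem to extend to Table 8.** The documents do not support that. The sentence precedes the citation of Table 8, and no single SD fits both RVEF rows at 24 and 12 patients: SD 8.37 matches 5.0 at 80% but gives 85% for 8.0 at n = 12, while SD 9.0 matches the latter but gives 74% for the former. No RVEF figures are offered here.

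**This is a pilot.** C8.p accepts a signal short of significance, C8.o mentions exploratory displays, and nothing says that a null subtype result will be taken as no effect. That limits the harm. It does not justify a specific power claim that the design does not secure.

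**Conclusion.** The power claim for subtype is not supported. Within a subtype, the 80% at 4 strain points holds only with at least 12 completers (about 11 if variance is pooled). In a smaller group it is about 72%, 59% and 43% at 10, 8 and 6, or 78%, 68% and 56% with pooling. Read literally as interaction power, it is about 56% at best and 45% at 6/18.

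These figures rest on an inferred SD of about 4.45, equal variance in the two subtypes and 24 completers. Because the subtype mix is unknown, they do not predict what the trial will have. A reader might also infer that the overall strain comparison or the within-sex figures are underpowered. The check shows no such thing: both reproduce. The point concerns a non-primary analysis and is worth correcting because the correction is cheap.

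**What to change.** In C8.p1:
- Delete the sentence that carries the sex figures over to subtype.
- State that subtype numbers are not fixed by the design.
- For example splits of 12/12, 10/14, 8/16 and 6/18, give both the within-subtype power and the treatment × subtype interaction power for strain, with the SD and test used.
- Label subtype results exploratory, report them as estimates with confidence intervals, and say that a non-significant result in the smaller subtype will not be read as no effect.

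The cost is a few lines of text and a less favourable stated power for subtype. No quota, additional patients or change in conduct is needed.
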